## 5.3 Statistical Adjustment for Superiority Testing

As described below, an interim probability calculation will be performed and the study's enrollment may be enhanced to increase the likelihood of demonstrating superiority for either the safety or effectiveness primary endpoints (or both). If enrollment is enhanced, the nominal p-values for the safety and/or effectiveness superiority hypotheses will be adjusted to preserve overall Type 1 error rate. A description of the adjustment will be provided in a separate document. Adjustment is not required for safety and effectiveness non-inferiority testing since no planned trial adaptation is anticipated for the non-inferiority hypotheses.

## 5.4 Study-Specific NIM

WATER will use a study-specific non-inferiority margin based on baseline IPSS score, as detailed below.

### 5.4.1 Baseline Scores in TURP Trials

Baseline scores are important because of their relationship to change score that represent “slight improvement” (see discussion below). Marszalek reported a meta-analysis of TURP trials (see Figure 1 and Table 1). The unweighted average mean baseline IPSS score in these TURP trials was 21, consistent with the American Urology Association’s 2011 guidelines document, which notes baseline IPSS scores in TURP trials “between 20 and 24.”

### 5.4.2 Change Scores in TURP Trials

In Marszalek’s group of TURP trials, the unweighted average IPSS change score at 12 months was 16 points. Because TURP has a large effect on IPSS scores, a “ceiling” effect is seen (wherein score changes reach their maximum). This results in a statistical relationship between baseline score and score change (Figure 4).

[figure not shown]

Figure 1. TURP trials reported in Marszalek.

Table 1. Trials included in Marszalek et al.

Author	Baseline IPSS	IPSS at 12 months	Improvement
Gupta	23.5	6	17.5
Kuntz	21	2.4	18.6
Montorsi	22	3.8	18.2
Westernberg	23	4	19
Wilson	24	5	19
Helke	18	5.5	12.5
Gupta	23.5	6	17.5
Nuhoglu	17.5	5	12.5
Seckiner	24	8	16
Hemmadeh	27	6	21
Shokeir	25.2	5	20.2
Van Melick	17	3.5	13.5
D'Ancona	17	3	14

De la Rosette	20	3	17
Wagrell	20.5	7.5	13
Hill	24.5	8	16.5
Kabalin	18	6.5	11.5
Martenson	22	3.5	18.5
Suvakovic	18.5	7.5	11
Non-weighted average	21.4	5.2	16.2

[figure not shown]

Figure 2. Relationship between baseline IPSS score and change score in TURP studies summarized in AUA 2003 document.

#### 5.4.3 Effect Size with No Treatment

FDA’s draft guidance document on non-inferiority margins (NIMs) in equivalence trials\* notes that NIMs should take into account not only the comparator treatment but also the treatment effect size, M1, i.e., the difference between treatment and no treatment. Non-inferiority trials are not supposed to use a NIM value larger than M1, the treatment effect for the comparator device.

For TURP, values for M1 are not available: there are no published placebo-controlled (or sham-controlled) trials of TURP. While in theory, the IPSS change score with no treatment in patients with moderate-to-severe BPH seeking surgical treatment is zero, several factors could contribute to non-zero changes, including regression to the mean, test-to-test variability, placebo effect, or spontaneous remission. Proxies for this “surgical placebo” change score are available. In placebo-controlled trials of alfuzozin, a commonly used alpha blocker, baseline scores were in the range of 17-19 and available change scores with placebo were 1.6 points, 4.2 points, 4.7 points and 4.9 points (see Figure 3). Meta-analysis of sham-controlled trials of endoscopic treatments for BPH (e.g., transurethral microwave thermotherapy) has shown a mean IPSS change score of about 6 points. Because subjects in sham trials are unaware of treatment, their expectations for improvement may be substantially higher than what would be observed with no treatment in

\* See <http://www.fda.gov/downloads/Drugs/.../Guidances/UCM202140.pdf>

standard clinical practice.\* We conclude that the IPSS change score in men with BPH seeking surgical treatment is likely to fall between 0 and 6 points. Therefore, the difference between the TURP change score and the no-treatment change score, i.e., M1 in FDA’s guidance document, is 10-16 points.

Note that the IPSS improvement resulting from BPH medication use is not relevant to WATER since WATER eligibility criteria require either failure of medical treatment or refusal of medical treatment.

**Table 3.1b. Efficacy and effectiveness outcomes in alfuzosin randomized, controlled trials**

Author, Year Study duration	Intervention (no. of patients assessed)	Baseline [mean (SD)]	Endpoint [mean (SD)]	Within group difference (within group P-value)	Between group difference (P-value)
Total International Prostate Symptom Score (I-PSS)					
Alfuzosin compared with placebo					
McNeill SA, 2005 6m	Alfuzosin 10mg QD (82)	NR	8.75(NR)	NR	Vs placebo: NR (P=0.012)
	Placebo QD (83)	NR	11.45(NR)	NR	NR
Roehrborn CG, 2001 3m	Alfuzosin 10mg QD (170)	18.2(6.3)	NR	-3.6 (NR)	Vs placebo: -2.0 (P=0.001)
	Alfuzosin 15mg QD (165)	17.7(5.7)	NR	-3.4 (NR)	Vs placebo: -1.8 (P=0.004)
	Placebo QD (167)	18.2(6.4)	NR	-1.6 (NR)	NR
Roehrborn CG, 2003 3m	Alfuzosin 10mg QD (473)	18.7(4.6)	12.7(6.1)	-6.0 (NR)	Vs placebo: -1.8 (P<0.001)
	Placebo QD (482)	18.8(4.4)	14.6(6.8)	-4.2 (NR)	NR
Roehrborn CG, 2006 2y	Alfuzosin 10mg QD (749)	19.2(4.7)	NR	-5.9 (NR)	Vs placebo: -1.2 (P=0.0017)
	Placebo QD (757)	19.2(4.7)	NR	-4.7 (NR)	NR
Van Kerrebroeck P, 2000 3m	Alfuzosin 10mg QD (137)	17.3(3.5)	10.4(4.7)	-6.9 (NR)	Vs placebo: -2.0 (P=0.002)
	Alfuzosin 2.5mg TID (147)	16.8(3.7)	10.5(6.1)	-6.4 (NR)	Vs placebo: -1.5 (P=0.02)
	Placebo QD (152)	17.7(4.1)	12.8(6.7)	-4.9 (NR)	NR
Alfuzosin compared with doxazosin					
De Reijke TM, 2004 14w	Alfuzosin 2.5mg BID/TID (87)	18.0(4.8)	NR	-7.5 (P<0.00)	Vs doxazosin: 1.7 (P<0.05)
	Doxazosin 1-8mg/day (93)	19.1(5.2)	NR	-9.2 (P<0.001)	NR

Figure 3. Alfuzosin trials summarized in AUA 2010 guideline.

#### 5.4.4 Barry’s Estimate of Slight Change

NIMs for BPH trials have historically relied on 1995 data from Barry et al, which describes men with mild-to-moderate BPH participating in a clinical trial of BPH medications. The specific purpose of Barry’s report was to note the correlation between IPSS change score and a global measure of improvement on a 5-point scale: marked, moderate, slight or no improvement, or worse. For each category of perceived improvement, the mean change score associated with that degree of global improvement was linearly related to baseline IPSS score (Figure 4). For the purposes of

\* A patient in a sham trial may think that he has a 50% (if 1:1 randomization) chance of having received the active treatment (vs. sham). This may result in change scores that are biased upwards compared to a patient who knows he is receiving non-active treatment only.

a non-inferiority clinical trial, the mean IPSS change representing “slight improvement” is most relevant and can serve as an appropriate NIM.

The mean IPSS improvement representing “slight change” was approximately 1 point for subjects with a score of 10 and 8 points for a baseline score of 30. Barry’s regression line describing this relationship is:

$$\text{Change score representing slight change} = -0.3636 * \text{IPSS}_{\text{base}} + 2.9091$$

where  $\text{IPSS}_{\text{base}}$  is the baseline IPSS score. (Roehrborn et al reported a very similar relationship in another BPH trial.) Barry’s finding makes clinical sense: a 1-point improvement in a patient with a baseline score of 30 would not be perceptible, whereas one-point improvement in a patient with a baseline score of 10, while small, is probably detectable.

[figure not shown]

Figure 4. Relationship between baseline IPSS and change score constituting various degrees of global improvement. Drawn on the figure are horizontal and vertical lines used to calculate the formula corresponding to the line for “slight improvement”: score change =  $-0.3636 * \text{IPSS}_{\text{base}} + 2.9091$

Barry et al highlighted that “the range of patient baseline scores must be considered when attaching a point value to a slight or moderate improvement rating.” Moreover, investigators “must describe patient baseline scores, which clearly influence how they perceive the subsequent score changes.” The strong and clear implication of these statements and Figure 4 is that interpretation of IPSS change scores needs to take into account baseline severity, as reflected in baseline IPSS scores. Moreover, because of the marked differences in target patient populations between Barry and WATER (Table 2), using Barry’s “slight improvement” mean IPSS of 3 points for WATER is scientifically invalid.

Table 2. Comparison of Barry and WATER

	Barry	WATER
IPSS entry criteria	≥8	≥12
What patients are seeking	Medications for BPH	Surgery for BPH*
Baseline IPSS score, mean	Approximately 16	Estimated 22**

\* Note that WATER excludes patients failing medical therapy or refusing medical therapy

\*\* Baseline IPSS scores in PROCEPT’s Phase 2 studies were >20

It is easily demonstrated that a cohort's mean IPSS change score perceived as "slight change" is mathematically directly related to the population's mean baseline IPSS score. Using Barry's regression line, we can calculate the expected mean score change representing slight change for a hypothetical group of men with BPH as:

$$(1) \text{ NIM} = \text{Mean Change for Slight Improvement} = \frac{\sum_{i=1}^N (m\text{Base}_i + b)}{N}$$

i.e., the sum of each man's threshold change score calculated from Barry's regression line ( $m = -.3636$ ,  $b = 2.9091$ ) and the man's baseline IPSS ( $\text{Base}_i$ ) divided by the sample size. Expanding (1):

$$(2) \text{ NIM} = \frac{\sum_{i=1}^N (m\text{Base}_i + b)}{N} = \frac{\sum_{i=1}^N m\text{Base}_i}{N} + \frac{\sum_{i=1}^N b}{N} = \frac{m \sum_{i=1}^N \text{Base}_i}{N} + b = \overline{m\text{Base}} + b$$

Equation (2) directly demonstrates that the mean IPSS change score representing "slight improvement" is linearly related to the mean baseline score ( $\overline{\text{Base}}$ ). The median baseline IPSS in Barry's cohort was 16, which, based on (2), corresponds to a change score representing slight improvement of approximately 3, i.e., the value reported by Barry (and applicable, we would argue, to his trial only). In TURP trials, with mean baseline scores of 20-24 (see Figure 1), the calculated change score for slight improvement would be 4.4 points for a 20-point baseline mean and 5.8 points for a 24-point baseline mean.

We will therefore calculate a study-specific NIM for WATER using (2) and the overall (both groups) baseline mean IPSS score. With an expected baseline mean IPSS score of about 23 (the mean baseline values in PROCEPT's phase 2 studies), the study-specific NIM would be approximately 5 points. This value represents the best literature-based estimate of the change score representing slight improvement in men with BPH seeking surgical treatment.

Note that FDA's guidance document on NIMs suggests choosing a NIM value (M2) that is substantially less than that of M1 such that the new treatment preserves most of the effect size compared to the standard treatment. Clearly, an M2 of approximately 5 points preserves most of TURP's effect size (10-16 points, see Section 5.4.3).

Based on FDA's feedback of August 26, 2016, an additional calculation will be made using a fixed NIM value of 4.7 points.

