## 5.2 Primary Effectiveness Endpoint

The primary effectiveness endpoint is the IPSS change score from baseline to 6 months. IPSS is an accepted and commonly used measure for symptom severity in BPH. IPSS varies from 0 (no symptoms) to 35 (maximal symptoms).

The difference in mean change scores will be calculated as  $D=D_A-D_T$ , where  $D_x$  signifies mean improvement from baseline, expressed as a positive number.  $D$  is the difference improvement; thus if the improvement is 14 points in A and 15 points in T, the difference  $D = -1$  point. The primary hypothesis is that of non-inferiority of 6-month change scores:

$$H_{0,E,N}: D=D_A-D_T \leq \text{NIM}$$

$$H_{A,E,N}: D=D_A-D_T > \text{NIM}$$

For these hypotheses, NIM is expressed as a negative number (e.g., -5 points). If non-inferiority is concluded, an additional test will be performed for statistical superiority:

$$H_{0,E,S}: D=D_A-D_T \leq 0$$

$$H_{A,E,S}: D=D_A-D_T > 0$$

The same notation is used for the last subscript: N = non-inferiority and S = superiority. Therefore, the 4 effectiveness hypotheses are:

- Null for non-inferiority
- Alternative for non-inferiority
- Null for superiority
- Alternative for superiority

A 2-sided 95% confidence interval for the difference in means will be used to test for non-inferiority. Non-inferiority will be declared if the entire 2-sided 95% CI is greater than the NIM (where NIM is expressed as a negative number). A gate-keeping strategy is used such that if the non-inferiority test is positive, a superiority test will be performed. A 2-sided  $(1-\alpha)\%$  confidence interval will be used to test for superiority. Superiority will be declared if the entire 2-sided 95% CI is greater than 0%. The sample size is fixed for the non-inferiority trial, but the sample size may increase (described below). For this reason, a multiplicity adjustment is required for the superiority analysis. Critical values will be chosen to ensure Type I error control.

The study will be deemed a non-inferiority success if both the safety and effectiveness primary endpoint null hypotheses are rejected. Additional analyses for the primary effectiveness endpoint will be performed using general linear models that incorporate potential predictors of IPSS change scores (e.g., baseline IPSS) as covariates. Subgroup analysis is described below.

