## 5.5 Sample Size Calculation

Sample size was reported in the original study protocol. Version G proposed an NIM of 4.7 points (based on an estimated baseline score distribution). With a sample size of 177 randomized subjects (118 A and 59 T), an effect size of -1.5 points, a standard deviation of 6 and a NIM of 4.7 points, the study has adequate power for the primary effectiveness endpoint. Power for the safety endpoint was also high assuming endpoint rates of 65% in T and 40% in A, including a 12% loss to follow-up rate.

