7. IPSS change score during follow-up (1 week, 1, 3, 6, 12, 24 and 36 months). Repeated measures analysis of variance (RMANOVA) will be used, with additional models that include baseline IPSS as a covariate. This analysis accounts for all available measurements and correlation of measurements within subjects. The mean differences across groups will be determined and the confidence limits from the regression model compared with the study-specific NIM. A treatment × time interaction will be explored as well. The purpose of this analysis is to evaluate whether the IPSS change score across all time points is non-inferior in A compared to T. The same NIM will be used as described for the primary effectiveness endpoint. If non-inferiority is shown, superiority will be tested. All available time points will be used up to month 36.
8. IPSS-QoL change scores (1 week, 1, 3, 6, 12, 24 and 36 months). A similar method as that with IPSS change score will be used and a 1-point NIM will be assumed.
9. Qmax change scores at 1, 3, 6, 12, 24 and 36 months. RMANOVA will be used.
10. PVR change scores at 1, 3, 6, 12, 24 and 36 months. RMANOVA will be used.
11. Proportion of subjects with device- or procedure-related adverse event. Proportions compared as described for primary safety endpoint.
12. Pelvic pain intensity level, population mean and change score mean, measured on a 0-10 numeric rating scale. Population score distributions will be compared with a Wilcoxon signed rank test. Change scores will be compared with a Wilcoxon test or t test. A non-inferiority margin of 2 points will be used.

13. EQ-5D time trade-off index (TTO) change scores during follow-up (7 days, and 1, 3, 6, 12, 24 and 36 months). TTO will be calculated using study data combined with available country-specific norms. RMANOVA will be used.
14. ISI at baseline, at post-op, 7 days, 1, 3, and 6 months. RMANOVA will be used.
15. IIEF-15 at baseline, and 7 days, 1, 3, 6, 12, 24 and 36 months. RMANOVA will be used.
16. MSHQ-EjD at baseline, 7 days, 1, 3, 6, 12, 24 and 36 months. RMANOVA will be used.
17. WPAI:US at baseline, 7 days, 1, 3, 6, 12, 24 and 36 months. Specifically, among those subjects who are currently working, the number of hours missed due to urinary symptoms will be compared. Given a large expected number of zeroes, a non-distributional method such as Wilcoxon's test will be used.
18. Pdet@Qmax at baseline and 6 months. This continuous outcome will be evaluated with a t test.

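### The protocol judges primary IPSS non-inferiority against a fixed 4.7 points, the SAP against a baseline formula (5.09 at mean 22, 5.45 at 23), and the supplied text does not say which governs

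*SAP*

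**What the plan says.** **Protocol.** The synopsis, 3.2 and 4.2 give one margin, 4.7 points, and 4.2 writes it into the null hypothesis as pre-specified. Section 4.4 powers the trial on it. The supplied protocol is Rev. H of 3 August 2020. It still carries 4.7 and marks the primary effectiveness endpoint as already reported.

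**SAP.** Section 5.4 opens with "WATER will use a study-specific non-inferiority margin based on baseline IPSS score, as detailed below". Section 5.4.4 sets the calculation: "We will therefore calculate a study-specific NIM for WATER using (2) and the overall (both groups) baseline mean IPSS score". The decision rule in 5.2 is "Non-inferiority will be declared if the entire 2-sided 95% CI is greater than the NIM", with no number attached. Section 7 item 7 compares later IPSS change with the study-specific margin and adds "The same NIM will be used as described for the primary effectiveness endpoint". Read together, these make the formula the SAP's primary margin. The fixed value survives in one sentence, added after FDA feedback of August 2016: "an additional calculation will be made using a fixed NIM value of 4.7 points". SAP 5.5 nevertheless states power at 4.7 and attributes that figure to the protocol: "Version G proposed an NIM of 4.7 points".

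**Precedence.** The nearest text is the last line of protocol 4.4, which leaves full analysis details to the SAP. It does not rank the documents or mention the margin.

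**The concern.** A primary non-inferiority test needs one threshold. Here the same confidence interval can pass under one document and fail under the other, whenever its lower limit falls between the two margins.

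The consequence goes beyond a label. Both the protocol synopsis and SAP 5.2 make study success depend on this verdict together with safety. SAP 6 tests its six secondary endpoints, intended for marketing claims, only if both primary endpoints meet their non-inferiority goals.

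The SAP text also understates the gap. "With an expected baseline mean IPSS score of about 23" it puts the margin at roughly 5 points, but its own formula gives 5.45 there. The distance from 4.7 is 0.75 points, not 0.3.

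**Working it through.** **Inputs**
- Formula slope -0.3636 and intercept 2.9091: SAP 5.4.4.
- Mean baseline IPSS 22 (SAP Table 2) or about 23 (SAP 5.4.4); 20 is the low end of the range cited in SAP 5.4.1.
- SD 6, true effect -1.5, 156 evaluable at 2:1, that is 104/52: protocol 4.4.
- One-sided 0.025, equivalent to the two-sided 95% CI: protocol 4.2, SAP 5.2.
- Up to 181 randomized and treated: protocol 2.11.

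**1. Reproduce the documents' own figures**
- Protocol margin: 1/3 × 1.9 + 2/3 × 6.1 = 4.70.
- SAP formula, as a positive number: margin = 0.3636 × mean - 2.9091. At 20 it is 4.36 and at 24 it is 5.82, matching the SAP's 4.4 and 5.8.
- Power at 4.7: SE = 6 × √(1/104 + 1/52) = 1.019; noncentrality (4.7 - 1.5)/1.019 = 3.14; noncentral t on 154 df gives 87.7%. This agrees with the protocol's statement of more than 80%.

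**2. Formula margin at the expected baselines**
- Mean 22: 7.9992 - 2.9091 = 5.09.
- Mean 23: 8.3628 - 2.9091 = 5.45.
- Equal to 4.7 at (4.7 + 2.9091)/0.3636 = 20.93.

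**3. Largest observed deficit that still passes (104/52)**

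Half-width of the 95% CI = 1.9755 × 1.019 = 2.013. Cutoff = margin - 2.013.

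| Margin | Cutoff | Power at -1.5 |
|---|---|---|
| 4.36 (mean 20) | 2.35 | 79.7% |
| 4.7 (protocol) | 2.69 | 87.7% |
| 5.09 (mean 22) | 3.08 | 93.8% |
| 5.45 (mean 23) | 3.44 | 97.1% |

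Observed deficits between 2.69 and 3.08 (or 3.44) pass under the SAP and fail under the protocol. At a mean of 20 the split reverses: deficits between 2.35 and 2.69 pass under the protocol only.

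**4. Chance of different verdicts (difference between the two pass probabilities)**

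| Analysed | True effect | Mean 22 | Mean 23 |
|---|---|---|---|
| 104/52 | -1.5 | 6.1% | 9.4% |
| 118/59 | -1.5 | 4.8% | 7.0% |
| 121/60 (assumed split of 181) | -1.5 | 4.6% | 6.7% |
| 104/52 | 0 | 0.3% | 0.4% |

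The two larger sizes assume no missing data. At a mean of 20 with 104/52 and -1.5, the reverse split is 87.7 - 79.7 = 8.0%.

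**5. Superiority**

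A CI wholly above 0 clears both margins. A split requires a lower limit between -4.36 and -5.45 over these baselines, so it cannot coincide with superiority.

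All figures use a nominal one-sided 0.025 for both documents. The protocol spends alpha at an interim look, while SAP 5.3 says "Adjustment is not required for safety and effectiveness non-inferiority testing since no planned trial adaptation is anticipated". That is a separate design difference and is left out here.

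**The case against.** **The SAP departed openly and already computes both.** It names the protocol's 4.7 and commits to a calculation against it. An analysis run under the SAP would therefore show any split, and protocol 4.4 gives the SAP some footing by leaving analysis details to it. This stands in part. What remains is which result is called primary, and leaving details to the SAP is not authority to replace a margin that the protocol calls pre-specified.

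**The planning sample overstates the risk.** This stands. Protocol 4.5.1 makes mITT primary, 4.7 imputes missing effectiveness data, and up to 181 subjects were treated. The split is then nearer 5% or 7%, although imputed data add less information than observed data.

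**A precedence statement may lie on removed pages.** This is possible, so the claim is limited to the supplied text.

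Three stronger readings are tempting, and the documents do not support them:
- *The margin was tuned to the results.* The formula is fixed in advance, uses only the pooled baseline mean, and is stricter than 4.7 below 20.93.
- *The SAP inflates type I error.* At a true deficit of 4.7 and 104/52, the formula margin declares non-inferiority 5.7% (mean 22) or 11.0% (mean 23) of the time, against 2.5%. That is an inflation only if 4.7 is the governing null, which is the open question. At its own boundary the formula margin holds 2.5%.
- *The protocol's 4.7 must have governed the reported analysis.* Nothing supplied shows which margin was applied, and SAP 5.5 using 4.7 for power does not rank the documents.

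**Conclusion.** The conflict is real and concerns the pass/fail threshold of the primary effectiveness endpoint. Within each document the primary margin is clear; what is missing is a rule between them. The chance of a different verdict is modest: 6% or 9% at 156 evaluable, about 5% or 7% at 177 to 181, and at most 0.4% at true equality for baseline means of 22 and 23. These figures rest on SD 6, a true effect of -1.5 unless stated, and the SAP's expected baselines. The observed baseline mean and result are not in the supplied text; if the reported interval clears both margins, the conflict has no effect on the conclusion. This should be fixed because study success and secondary testing depend on it. It does not by itself discredit the reported result.

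**What to change.** Issue a dated reconciliation note and leave the existing SAP text on record. The note should:
- state which margin was applied to the reported 6-month primary analysis and when that choice was fixed;
- give the difference and its 95% CI against both 4.7 and the formula value at the observed pooled baseline mean;
- if the verdicts differ, say whether the protocol's pre-specified 4.7 criterion was met, and not present non-inferiority without that qualification.

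It should not declare after the fact that 4.7 governed if the record shows that the formula was used.

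For IPSS analyses not yet reported, name one primary margin in both documents. The fixed 4.7 is the natural candidate: it is the protocol's hypothesis and the stated power basis, and 88% power with 156 evaluable stays above the stated 80%.

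The cost is one note and one additional display, and the SAP already commits to the 4.7 calculation. The downside is that 4.7 is the stricter margin at the expected baselines, costing 93.8 - 87.7 = 6.1 to 97.1 - 87.7 = 9.4 percentage points of power. At a baseline mean of 20 it would be the easier margin (87.7% against 79.7%).
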